Study Protocol

Project Title:

Version Date:

Skeletal muscle atrophy and dysfunction following total knee arthroplasty

3-23-22

NCT number:

NCT03051984

**Principal
Investigator
(contact):**

[name]

Grant Sponsor:

NIA R01 AG050305

PROTOCOL SUMMARY

Knee osteoarthritis (OA) is the leading cause of disability in older adults. Because non-surgical therapies are inadequate in managing symptoms and do not alter the disease course, total knee arthroplasty (TKA) is an important final treatment option. While TKA alleviates joint pain, objectively-measured physical function does not improve much beyond pre-surgical levels. Moreover, it often takes 1-2 years to recover to function to pre-surgical levels. TKA fails to correct disability, in part, because of the precipitous decline in lower-extremity neuromuscular function in the early, post-surgical period, forcing patients to first overcome the disabling effects of the procedure before redressing pre-surgery functional deficits. Surprisingly, very little is known about the nature of muscle structural and functional adaptations during the early, post-surgical period, aside from a small number of studies at the whole muscle level suggesting decreased neural activation as the major cause of dysfunction. To address these gaps in scientific knowledge and clinical treatment options early following TKA, our goals in this project are to: 1) to comprehensively examine, from the molecular to the whole body level, skeletal muscle structural and functional adaptations following TKA and 2) to assess the utility of neuromuscular electrical stimulation (NMES) to counter early, post-surgical muscle adaptations. Based on our preliminary data, we hypothesize that TKA causes profound reductions in skeletal muscle size and intrinsic function during the early, post-surgical period that contribute to long-term functional disability and that these adaptations can largely be prevented by NMES. To accomplish our goals, we will study patients with advanced-stage knee OA prior to and 5 following surgery who are randomized to receive NMES or no intervention during this period. All volunteers will receive standard of care physical rehabilitation during this period. Tissue acquired from skeletal muscle biopsies will be used to characterize skeletal muscle myofilament and mitochondrial structure and function, in combination with assessments of whole muscle and body functional capacity. If successful, our results could shift conventional thinking in this field away from the role of neural adaptations as a cause of post-surgical disability and emphasize the importance of muscle atrophy and intrinsic myofilament function. Additionally, our data on the utility of NMES to prevent such adaptations may provide important mechanistic data to support this modality as a new transitional rehabilitative care intervention to improve long-term functional prognosis in TKA recipients.

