Effects of TKA on skeletal muscle structure and function. Physical function declines rapidly and profoundly in the early, post-surgical period following TKA (8, 24). One determinant of the TKA-related reduction in physical function is lower extremity muscle weakness (15, 16, 25). Data from our labs and others show that reductions are most prominent in the quadriceps, where strength declines >50% early, post-surgery (15, 25-27). Conventional wisdom holds that deficient neural activation is the primary factor driving muscle weakness, with a much smaller contribution from intrinsic muscle adaptations, such as atrophy (15). However, studies at the whole muscle level are insufficient to define muscle-specific adaptations because of methodological limitations (eg, whole muscle imaging techniques underestimate muscle atrophy compared to single fiber assessments) and confounding factors (eg, impaired neural activation and antagonist muscle co-contraction impair whole muscle strength measures). Regarding the latter, using single muscle fibers, we have shown, for the first time, profound (~30-50%) deficits in contractility early following TKA at the cellular level, including reductions in tension (ie, force/CSA) and velocity in MHC IIA and IIX fibers. Such contractile deficits likely contribute to whole muscle/body functional deficits, as MHC II fibers are important determinants of dynamic muscle function (28).

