For NMES to improve disability in TKA recipients, it should address the mechanisms underlying persistent functional deficits. While impaired neural activation is widely believed to drive early, post-surgical reductions in muscle strength (15), these deficits regress rapidly, with near complete correction within 3-6 months (46). In contrast, intrinsic muscle adaptations are thought to remediate more slowly, contributing disproportionately to long-term functional deficits (15, 19, 20). Thus, while NMES may improve early functional deficits due to impaired neural activation (47, 48), as our data show (46), to impact long-term disability it needs to prevent atrophy and intrinsic contractile dysfunction during the early, post-surgical period. To this end, our preliminary data provide the first direct evidence of effects of NMES on muscle fiber size and function in TKA recipients. We found that early use of NMES diminishes fiber atrophy in MHC I and II fibers and improves myofilament protein function in MHC II fibers, with a surprising improvement in contractile velocity (+23%) after 5 wks. The combined effect of improved tension and velocity may mitigate reductions in whole muscle power output (power= force X velocity) that predispose to disability (49). These effects of NMES on single muscle fiber size and MHC II fiber function, particularly improvements in contractile velocity, which are increasingly thought to be at the root of deficits in muscle power that promote disability (50), may ameliorate the precipitous decline in lower extremity function in the early post-surgical period following TKA.

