Single fiber function will be assessed on segments of chemically-skinned muscle fibers, as used routinely by our lab. Cellular function will be measured on chemically-skinned, fiber segments, including force, velocity and power, as described by us (1) and molecular function (myosin-actin cross-bridge kinetics/mechanics) by sinusoidal analysis, as pioneered in human skeletal muscle by our lab (5). These measures will be available on the most abundant fiber types: MHC I, IIA and IIX (>90% of fibers in cancer patients (6)).

Single fiber cross-sectional area (CSA) will be measured by IHC, as described (1), with the addition of MHC IIA and IIX antibodies to delineate MHC II sub-types, as described (7), as these comprise the majority of fibers (MHC I, IIA, IIX; >90%) in cancer patients (2).

Mitochondrial content/morphology (sub-sarcolemmal and intermyofibrillar: % content, size, # per unit area/sarcolemmal length) and myofibrillar ultrastructure (myofibrillar % area, A-band length) will also be assessed by EM, as described by us (2, 6).

Accelerometry will be performed (5 d each): at baseline and ~weekly throughout the 5 week intervention, as described (12). This will be accomplished using an Actigraph waist-worn accelerometer.

Thigh muscle size and body composition will be measured, as described (13), to track changes in body composition and quadriceps muscle CSA by CT to characterize differential changes between legs, as described (2).

Thigh muscle function will be assessed by isokinetic/isometric dynamometry, as described (12), to characterize changes in whole muscle function (isometric: 70°; isokinetic: 60 and 180 °/sec), adjusted for quadriceps CSA, with central neural activation assessed by the interpolation technique, as described by us (14).

Whole body function will be assessed using the 30 second sit-to-stand test, timed up and go (TUG), stair climb (SCT) (16) and the Short Physical Performance Battery (SPPB) (17, 18), as described by us (19, 20).

Blood samples will be taken to examine circulating factors that may contribute to muscle atrophy and/or dysfunction.

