An individual research record will be kept on each volunteer in compliance with HIPAA standards. This record will contain identifying data, demographic information and results from all clinical research measurements and evaluations. The results of all testing will be kept confidential. In addition, skeletal muscle tissue samples will be taken and will be used for measurement of muscle size, structure and function. All materials gathered in conjunction with the proposed studies will be used for research purposes only and will be available only to research personnel working on these studies, who have obtained proper training in human subjects research and privacy protection.

DRUG AND DEVICE INFORMATION

Drug (s)	 Not applicable
Device (s)	 Not applicable

Device name and indications

The interventional device used in this study: EMPI Continuum complete electrotherapy system has received FDA approval (501K: K093324) for retarding disuse-related atrophy, which we believe is one of the primary mechanisms whereby muscle adaptations evolve in TKA recipients in the early, post-surgical period. That is, muscle disuse secondary to pain, limited range of motion and muscle weakness

(the latter being due to neural inhibition caused by joint pain/swelling) causes skeletal muscle fiber atrophy and weakness and mitochondrial rarefaction and dysfunction.

Is it FDA approved:

Yes. It is approved to mitigate muscle atrophy/dysfunction associated with muscle disuse (501K: K093324) (see Appendix 3).

Risk assessment (non-significant/significant risk)

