Statistical Analytical Plan

Project Title:

Skeletal muscle atrophy and dysfunction following total knee arthroplasty

Version Date:

3-23-22

NCT number:

NCT03051984

**Principal
Investigator
(contact):**

[name]

Grant Sponsor:

NIA R01 AG050305

For Aim 1, using pre-surgery and 5 wk post-TKA assessments in the control group, we will assess the effect of TKA (pre- vs. 5 wk post-TKA) on muscle fiber size and function. Primary outcomes include: single muscle fiber CSA for MHC I and IIA fibers and tension and velocity for MHC I and IIA fibers, and IMF and SS mitochondrial content. We will use a general linear mixed model, with a random effect to account for observations clustered within patients (eg, single fiber CSA and function), with the model conceptualized as a multi-level analysis with single fiber values comprising level 1 variables and whole muscle or person-level covariates comprising level 2 variables (130). Covariates (eg, baseline value, etc.) can be included in the model as level 2 variables to determine if variation in any primary outcome is related to variability in these factors. Additionally, we can include sex in the model to examine whether the effects of TKA differ between men and women. In secondary analyses, we will examine whether changes in muscle fiber size or functional mediate changes in whole muscle and body function using mediation analysis, if effects of TKA are noted in the latter. Such analyses seeks to determine whether the effect of an independent variable or intervention (TKA) on some outcome variable (whole muscle/body function) can be transmitted through a third variable, referred to as a mediator (single fiber CSA or function). Variables with multiple observations per subject will be collapsed into a single mean value.

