For Aim 2, pre- and 5 wk post-surgery data will be compared between volunteers randomized to NMES and control interventions. Our primary analysis will assess treatment effects (group X time interaction) on muscle structural and functional variables. Primary outcomes are identical to Aim 1 and will be similarly evaluated using a general linear mixed model, as described above, with group (NMES vs. control) and time (pre vs. 5wks post-TKA) as between- and within-subject factors, respectively. Potential confounding factors will be compared between groups and factors that differ can be included into the model as level 2 covariates. We assume that dropouts will be random, but will examine whether they differ from volunteers completing the study. Moreover, we can conduct sensitivity analysis on dropouts, assuming the most and least conservative responses, to assess their impact on study outcomes. Additionally, we can include sex as an additional effect in these models to determine if NMES effects differ by sex. In secondary analyses, we will also examine the effect of treatment on whole muscle/body functional measures. If there are effects of NMES to maintain whole muscle/body functionality at 5 weeks, we will examine whether changes in single fiber structural or functional outcomes partially or completely mediate whole muscle/body functional improvements with NMES using mediation analysis.

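### The secondary mediation analyses use muscle fiber measures as the only mediator, so if fiber and activation changes are correlated, part of any activation effect will be credited to fibers

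*SAP*

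**What the plan says.** **SAP, Aim 1.** If TKA affects whole muscle or body function, mediation analysis will examine whether that effect "can be transmitted through a third variable, referred to as a mediator (single fiber CSA or function"). This uses the control group, before surgery and at 5 weeks.

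**SAP, Aim 2.** If NMES maintains function at 5 weeks, the plan is to test whether "changes in single fiber structural or functional outcomes partially or completely mediate whole muscle/body functional improvements with NMES using mediation analysis".

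Both analyses are secondary, and both depend on a functional effect being found first. Activation is not listed in the SAP as mediator, covariate or outcome.

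**Protocol on activation.**
- Background for Aim 1 reports the prevailing view: "Conventional wisdom holds that deficient neural activation is the primary factor driving muscle weakness". In the authors' own voice, it also lists impaired activation among the factors that confound whole muscle strength measures.
- Background for Aim 2 says the activation deficits recede quickly and are nearly gone within 3-6 months. It adds that, "while NMES may improve early functional deficits due to impaired neural activation (47, 48), as our data show (46"), a lasting benefit requires protecting the muscle itself.
- Thigh muscle function testing is done "with central neural activation assessed by the interpolation technique, as described by us (14"). The 5-week visit repeats the pre-surgery tests, so activation change is available over the same interval as fiber change.
- The Protocol Summary says that, if successful, the results could "shift conventional thinking in this field away from the role of neural adaptations as a cause of post-surgical disability".

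**The concern.** Randomisation protects the estimated effect of NMES on fibers and its effect on function. It does not protect the step from fiber change to function change, which is an observational association within arms. A variable that affects function and is correlated with fiber change confounds that step if it is left out.

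The protocol's own account makes activation such a candidate: it affects strength, and NMES may change it. The device section also links it to fiber loss. There, disuse follows from pain, restricted motion and weakness, with "the latter being due to neural inhibition caused by joint pain/swelling", and disuse in turn causes fiber atrophy. That makes a non-zero correlation plausible, but its size is not given.

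At stake is the reading of a positive mediation result. A statement that fibers partly or fully explain preserved function could be reported when some or all of the effect ran through activation. Even with no correlation, a fiber-only model leaves the activation effect inside an unlabelled direct effect, so it gives no estimate of the neural share.

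**Working it through.** **Sample size used.** The protocol randomises 32 per group, expecting 25% attrition. Check: 24 / (1 - 0.25) = 32, which reproduces. The simulations use 24 per group. The documents give no alpha, effect size, SD or fiber-activation correlation for these analyses, so the remaining inputs are assumptions.

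**Assumptions (Aim 2).** With g = 1 for NMES and 0 for control, all in SD units of change:
- fiber change F = 0.8g + z1 and activation change A = 0.8g + z2, with within-arm correlation r between z1 and z2;
- function change Y = cA + error, c = 0.5 or 0.7, error variance 1 - c². The true fiber path is zero;
- two-sided 5% tests; mediation is declared when both the NMES-to-fiber and fiber-to-function paths are significant.

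**Size of the bias.** Regressing Y on g and F gives an expected fiber coefficient of c × r.
- Apparent indirect effect = 0.8 × c × r.
- Total effect = 0.8 × c.
- Falsely mediated share = r × (NMES effect on F / NMES effect on A) = r × (0.8 / 0.8) = r.

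So the share is 0 at r = 0, about 30% at r = 0.3 and about 50% at r = 0.5, whatever c is.

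**How often false mediation is declared, before the functional-effect condition.**

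| r | c = 0.5 | c = 0.7 |
|---|---|---|
| 0.1 | 5% | 6% |
| 0.3 | 13% | 23% |
| 0.5 | 31% | 52% |

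With activation in the model the rate is about 3-4%.

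**Applying the SAP's condition.** Aim 2 mediation is run only if NMES affects function. Reading that as p < 0.05, the effect of 0.8c is detected in about 28% of trials at c = 0.5 and 48% at c = 0.7. A rough product gives 0.28 × 13% ≈ 4% (c = 0.5, r = 0.3) and 0.48 × 52% ≈ 25% (c = 0.7, r = 0.5). Direct simulation gives about 4% and 27%; the upper figure exceeds the product because the two events are positively associated.

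**When fibers do matter.** Take true coefficients of 0.3 for fiber and 0.6 for activation.
- True fiber share = (0.8 × 0.3) / (0.8 × 0.3 + 0.8 × 0.6) = 0.24 / 0.72 = 33%.
- Fiber-only share at r = 0.3: 0.8 × (0.3 + 0.3 × 0.6) / 0.72 = 0.384 / 0.72 = 53%.
- Fiber-only share at r = 0.5: 0.8 × (0.3 + 0.5 × 0.6) / 0.72 = 0.48 / 0.72 = 67%.
- With activation entered, the simulated fiber indirect effect is 0.24-0.25, about 33% at every r.

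**Aim 1.** Regressing function change on fiber change in 24 controls, again with no true fiber path, gives a falsely significant fiber path in 10% to 40% of trials at r = 0.3-0.5, and about 5% with activation entered.

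**Imperfect measurement.** The correction above assumes activation is measured without error. At an assumed reliability of 0.7, the fiber path in the Aim 2 model is still falsely significant in about 6% (c = 0.5, r = 0.3) to 16% (c = 0.7, r = 0.5) of trials.

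**The case against.** The strongest reply is that the design already deals with the neural question where it counts. The primary outcomes are measured on fibers and mitochondria; single fiber function in particular is measured on skinned segments, out of reach of central activation. The protocol also tests function at 6 months, when it expects activation to be nearly normal, to see whether early effects predict later function. Neither aim promises to apportion neural and muscle shares. **This stands for the primary analyses.** It does not rescue the 5-week mediation models, and the SAP specifies no 6-month model.

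A second reply is that covariates may be added. In the SAP, though, covariates are optional and belong to the mixed models for the primary outcomes. For Aim 2 they are prompted by a difference between groups. Nothing commits to activation in the mediation model.

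A third is that the effect sizes and r are invented, and that a zero fiber path is the case least favourable to the plan. **This stands.** The figures show what could happen, and at r = 0 the fiber estimate is unbiased.

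Some stronger readings are tempting, and the documents do not support them:
- *Weakness at 5 weeks is mainly neural.* The backgrounds report this as the prevailing view, which the trial sets out to challenge. The device section does attribute weakness to neural inhibition, but with no 5-week figure or apportionment.
- *Activation stays impaired until 3-6 months.* The protocol stresses rapid recovery, nearly complete within that window. How much deficit remains at 5 weeks is not stated.
- *NMES certainly improves activation in this trial.* The protocol says it may, citing the group's earlier data.

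**Conclusion.** The point holds in a conditional form. Both mediation analyses omit a measured variable that the protocol itself says affects strength and may respond to NMES. If its change correlates with fiber change within arm, the fiber share is overstated. Under the stated assumptions the overstatement is 30-50% of the NMES effect at r = 0.3-0.5, with false mediation in about 4-27% of all trials.

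A reader might take the 13-52% range as a rate over all trials. It is not, because the SAP runs the Aim 2 analysis only after a functional effect is found. A reader might also infer that the whole trial cannot address muscle adaptation. That goes too far: the primary fiber and mitochondrial comparisons are untouched. What the fiber-only model cannot support is a claim that muscle rather than neural change explains *function*.

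Because the analyses are secondary and conditional, this is a worthwhile correction to the SAP and no threat to the trial's main inference.

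**What to change.** In the SAP mediation analyses for both aims, when the outcome is strength or whole body function:
1. Enter change in central activation (interpolation technique, pre-surgery to 5 weeks) as a parallel mediator beside the fiber measure.
2. Report the fiber and activation indirect effects with intervals, and label them exploratory.
3. Base any muscle-versus-neural statement about function on this model only.
4. State that measurement error in activation, and other confounders of the fiber-to-function path such as pain, swelling and disuse, may leave residual bias.

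The cost is SAP wording and modest analysis time; the activation data are already collected. The statistical price is one more parameter and a somewhat wider interval for the fiber path, which matters at 24 per group.

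### The mediation analyses treat the change in a patient's mean fiber value as error-free, so a complete mediation can read as partial, and the plan gives no fiber counts or variances to judge by how much

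*SAP*

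**What the plan says.** The Aim 1 part of the SAP first sets out the primary analysis, a mixed model on individual fiber values, "with a random effect to account for observations clustered within patients (eg, single fiber CSA and function". It then adds a secondary step: "we will examine whether changes in muscle fiber size or functional mediate changes in whole muscle and body function using mediation analysis". This step is run only if an effect of surgery on whole muscle or body function is seen. The paragraph closes with the rule "Variables with multiple observations per subject will be collapsed into a single mean value".

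The Aim 2 part does the same for the intervention, again only if a functional benefit is found: "we will examine whether changes in single fiber structural or functional outcomes partially or completely mediate whole muscle/body functional improvements with NMES". It does not repeat the collapse rule. I take the rule to carry over, because no other is given.

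The Protocol (Procedures, Aim 1, Pre-surgery testing) shows that the candidate mediators come from different assays. "Single fiber cross-sectional area (CSA) will be measured by IHC", whereas "Single fiber function will be assessed on segments of chemically-skinned muscle fibers". Neither document gives the number of fibers per biopsy for either assay, a within- or between-patient variance, or any correction for error in the mediator.

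**The concern.** A mean over a limited number of fibers estimates the patient's true fiber size or function with sampling error, and a change between two biopsies carries that error twice. In an ordinary mediation regression, random error in the mediator leaves the effect of treatment on the mediator unbiased. It shrinks the slope from mediator to outcome, and the part that is lost reappears as direct effect.

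The Aim 2 question is whether mediation is partial or complete, and that is the reading most exposed to this shrinkage. The Protocol Summary hopes to move attention from neural adaptation to atrophy and intrinsic fiber function. An inflated direct path could be taken as support for the neural explanation when it only reflects how few fibers were measured. If precision differs between fiber area and fiber tension or velocity, a side-by-side reading of their mediated shares would partly compare assays.

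**Working it through.** **Plan's own figure.** The documents give no figure for the mediation analysis. The only sample-size figure (Protocol, Methods and Procedures) reproduces: 24/(1 − 0.25) = 32 per group. So about 24 patients per group are expected for Aim 2, and about 24 controls for Aim 1.

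**Attenuation.** Let λ be the reliability of the change in the patient mean, within treatment group. With one mediator, a linear model, random error and no mediator-outcome confounding, where a is the effect on the mediator, b the mediator-to-outcome slope and c′ the direct effect:

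- estimated indirect effect = a·b·λ
- estimated direct effect = c′ + a·b·(1 − λ)
- estimated mediated share = true share × λ

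For Aim 1 (controls only, before versus after surgery) the same holds, with a as the mean change in the mediator and b as the slope of change on change.

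**Reliability, first set of assumptions.** None of these inputs is in the documents: within-patient fiber coefficient of variation (cv) 0.25 to 0.35; SD of true change (t) 0.10 to 0.20 of the mean; m fibers per biopsy.

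λ = t² / (t² + 2·cv²/m)

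| t | cv | m = 10 | m = 50 |
|---|---|---|---|
| 0.15 | 0.25 | 0.0225/(0.0225 + 0.0125) = 0.64 | 0.0225/(0.0225 + 0.0025) = 0.90 |
| 0.15 | 0.35 | 0.0225/(0.0225 + 0.0245) = 0.48 | 0.0225/(0.0225 + 0.0049) = 0.82 |
| 0.10 | 0.35 | 0.01/(0.01 + 0.0245) = 0.29 | 0.01/(0.01 + 0.0049) = 0.67 |
| 0.20 | 0.25 | 0.04/(0.04 + 0.0125) = 0.76 | 0.04/(0.04 + 0.0025) = 0.94 |

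Each entry is also the share that would be expected if the truth were 100% mediation.

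**Reliability, second set of assumptions.** This uses the intraclass correlation of fibers within patient (ICC), the correlation r between true patient means before and after surgery, and k fibers per visit. All are assumed.

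λ = ICC(1 − r) / [ICC(1 − r) + (1 − ICC)/k]

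At ICC 0.2 and r 0.5:

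- k = 10: 0.1/(0.1 + 0.08) = 0.56
- k = 20: 0.1/(0.1 + 0.04) = 0.71
- k = 100: 0.1/(0.1 + 0.008) = 0.93

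A true share of 50% is then expected to read 28%, 36% and 46%. Simulation with 24 per group and 20,000 replicates gave the same values. Over ICC 0.1 to 0.5, r 0 to 0.8 and k 5 to 200, λ runs from 0.10 to about 1.00.

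**Size against function.** At r 0.5 and a true share of 50% for each mediator taken alone:

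- ICC 0.2 for both, 100 size fibers and 10 function fibers: 46% for size, 28% for function.
- Size ICC 0.05 with 50 fibers (λ 0.57), function ICC 0.4 with 20 fibers (λ 0.87): 28% for size, 43% for function.

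The order follows the variances as well as the counts.

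**When the conditions fail.** Two correlated mediators in one model (true indirect effects 0.30 each, correlation 0.5, λ 0.9 and 0.5) give estimates of 0.34 and 0.14. With an unmeasured common cause of mediator and outcome (mediator loading 0.6, λ 0.9), a true share of 50% is estimated at 99%.

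**The case against.** The case against giving this much weight is substantial. The analysis is secondary and runs only if a functional effect appears. The primary models keep fiber-level data. Every input above is assumed, and the resulting range covers both serious attenuation and almost none. The Aim 1 hypothesis itself expects fiber changes to explain impairment only in part, so complete mediation is a benchmark there and not the plan's prediction. A latent multilevel mediation model as the main analysis would be fragile at about 24 patients per group. All of this stands, and it limits the weight of the point and the remedy.

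Three stronger readings are tempting, and the documents do not support them:

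- **Collapsing creates the error.** It does not. The error comes from measuring few fibers, and averaging reduces it: at ICC 0.2 and r 0.5, λ is 0.1/(0.1 + 0.8) = 0.11 with one fiber and 0.56 with ten. What is missing is an error model for the mean.
- **Fiber size will look like the stronger mediator because more fibers are counted for it.** No count is given for either assay, no ranking of size against function is planned, and the second comparison above reverses the order.
- **The mediated share is bound to be underestimated.** That holds only under the stated conditions. The mediator is not randomized and Aim 1 has a single group, so confounding may push the share upward, as may correlated mediators for the better-measured one.

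None of this makes the change in the mean free of error, or supplies the reliability needed to interpret the share.

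**Conclusion.** The point holds in limited form. The plan treats the change in a finite-sample mean as exact in an analysis meant to say whether mediation is partial or complete. Under one mediator, linearity, random error and no mediator-outcome confounding, the share shrinks by the factor λ, so complete mediation would be expected to read as partial. The documents cannot fix the amount. The first set of assumptions gives 0.29 to 0.76 with 10 fibers per biopsy and 0.67 to 0.94 with 50. Those figures leave out variation between biopsy sites, which would lower reliability further.

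Reliability may differ between fiber area and tension or velocity, so their shares should not be compared directly; the direction of any distortion is unknown. The primary analyses and the sample size are untouched. This is an inexpensive improvement to a secondary, conditional analysis.

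**What to change.** Keep the collapsed-mean mediation analysis and add the following to the SAP for both aims:

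1. For each mediator, report beside it a reliability-corrected estimate by regression calibration. The error variance of a patient's change is s²/m at the first visit plus s²/m at the second, using that patient's own fiber count m at each visit.
2. Take s² as the variance among fibers within one biopsy and one fiber type. Do not use the residual of a model with a single random intercept per patient: it also absorbs patient-by-time variation, which is part of the true change, and would overcorrect.
3. Report fiber counts and estimated reliability by measure and visit.
4. Do not describe mediation as partial or complete, or compare size with function, on the uncorrected estimate alone.

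The fiber data needed are already to be collected. The cost is SAP wording, some programming and wider intervals for the indirect effect. The correction does not remove mediator-outcome confounding and can enlarge a confounded slope: the 99% above becomes 0.99/0.9 = 110%. The report should say so wherever the corrected estimate appears.
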